### **Stool Frequency**

The following formula should be used for calculating the Mayo stool frequency sub score:

CCI - This section contained Clinical Outcome Assessment data collection questionnaires or indices, which are protected by third party copyright laws and therefore have been excluded.

CCI - This section contained Clinical Outcome Assessment data collection questionnaires or indices, which are protected by third party copyright laws and therefore have been excluded.									

### Rectal Bleeding

The rectal bleeding sub score will be the average of the daily scores, rounded.

The following table illustrates day selection and RB calculation under different scenarios. The daily score calculated in the example would be reported day -1 for daily scores but used for the calculation of the Partial Mayo score on the Day 1 visit.

Example	Diary Day							Valid days for calculation of scores	Notes	Average sub-score	RB
	-7	-6	-5	-4	-3	-2	-1				
A	3	1	2	2	3	M	3	-3,-4,-5	Consecutive > recent	2.33	2
B	3	1	2	2	M	2	3	-4,-5,-6	Consecutive > recent	1.67	2
C	3	1	2	M	3	2	3	-1,-2,-3		2.67	3
D	3	1	2	X	E0	E1	3	-5,-6,-7		2.00	2
E	3	1	M	M	X	E0	E1	Missing (primary analysis); -7,-6 (sensitivity analysis)		2.00 (in the sensitivity analysis)	2
F	3	1	M	M	2	M	2	-1,-3,-6	3 days recent	1.67	2
G	3	1	2	M	2	X	E0	-5,-6,-7	Consecutive > recent	2.00	2
H	3	1	2	M	2	2	M	-5,-6,-7	Consecutive > recent	2.00	2

Example	Diary Day							Valid days for calculation of scores	Notes	Average sub- score	RB
	-7	-6	-5	-4	-3	-2	-1				
I	M	1	M	M	X	E0	E1	Missing		.	.

M = Missing, X = Bowel prep, E0=Endoscopy, E1=Day after endoscopy

### **Absolute Stool Number**

The calculation of absolute stool number will follow the same methodology as the calculation of the rectal bleeding sub score.

Note that the categorisation of Mayo sub scores is defined above along with full Mayo score definitions.

#### **15.6.3.3. Endoscopy scores**

Clinical Efficacy
UCEIS
CCI - This section contained Clinical Outcome Assessment data collection questionnaires or indices, which are protected by third party copyright laws and therefore have been excluded.

**Clinical Efficacy**

CCI - This section contained Clinical Outcome Assessment data collection questionnaires or indices, which are protected by third party copyright laws and therefore have been excluded.

The following endpoint for the UCEIS is to be considered at each visit:

- **UCEIS Total Score:** Sum of all likert scale anchor points scores (this will range from 0 – 8).

**15.6.3.4. Histology scores****Geboes**

CCI - This section contained Clinical Outcome Assessment data collection questionnaires or indices, which are protected by third party copyright laws and therefore have been excluded.

CCI - This section contained Clinical Outcome Assessment data collection questionnaires or indices, which are protected by third party copyright laws and therefore have been excluded.

### Robarts Histology Index (RHI)

The RHI will be derived by GSK as an additional tool to measure histologic disease activity using the following two tables to derive the RHI from the Geboes sub-scores.

#### Mapping of Geboes score to Robarts Criteria

Geboes Score		Robarts Criteria	Robarts Multiplier
--------------	--	------------------	--------------------

CCI - This section contained Clinical Outcome Assessment data collection questionnaires or indices, which are protected by third party copyright laws and therefore have been excluded.

CCI - This section contained Clinical Outcome Assessment data collection questionnaires or indices, which are protected by third party copyright laws and therefore have been excluded.

### Robarts Histology Index Conversion from Geboes

CCI - This section contained Clinical Outcome Assessment data collection questionnaires or indices, which are protected by third party copyright laws and therefore have been excluded.

The RHI Score is a continuous score, ranging from 0-33 with higher scores indicating more severe disease. The following categorical endpoints are derived from this score:

- “**RHI Remission**” will be defined as an RHI score  $\leq 6$
- “**RHI Deep Remission**” will be defined as an RHI score  $\leq 3$

[figure not shown]
### Nancy Index

The Nancy Index will be provided by Robarts as an additional tool to measure histological disease activity.

**CONFIDENTIAL**

204869

CCI - This section contained Clinical Outcome Assessment data collection questionnaires or indices, which are protected by third party copyright laws and therefore have been excluded.

### 15.6.3.5. Intercurrent Events Selection

If more than one intercurrent event occurs for a subject, then the earliest event will be considered for reporting. If two events occur at the same timepoint, then (for the respective Estimand) the event listed first in the list below will be prioritized:

- Secondary Efficacy Estimand:
  - Discontinuation from IP
  - Valid endoscopy result not available
  - Excluded medication

Note that no distinction is made in the above list between COVID-related discontinuations, discontinuations due to sponsor's decision to terminate the study and other discontinuations, as they are mutually exclusive and a participant can only experience one of these three ICEs. For the same reason, a list for the Primary Efficacy Estimand is not needed.

### 15.6.4. Safety

Adverse Events
Exposure Adjusted Incidence Rates

 
○ For selected Preferred Terms, the exposure adjusted incidence rate of AEs will be reported within a study phase. Derive the exposure adjusted incidence rate as :           
Subject months (Person months) = sum of subject total exposure duration in days for a study phase (across all subjects)/30.4375, where subject total exposure duration in days is calculated as below –
 
 
○ if they DO experience the AE, then start date of first AE – treatment start date of the study phase + 1.
 
○ if they DO NOT experience the AE, then treatment stop date of the study phase – treatment start date of the study phase + dose specific days (Refer to Section 15.6.2 : Study Population/Duration of Exposure)
 
 
Number of subjects with event per 100 subject-months = 100*number of subjects with event in the study phase/subject months.
 
Note that an event is only counted once per subject.
 
 

ECG Parameters
RR Interval

 
• If RR interval (msec) is not provided directly, then RR can be derived as: <math>(1/HR)/1000</math>(i.e. 1 / heart rate where the heart rate is taken as part of the ECG)
 
• If ECGs are manually read, the RR value preceding the measurement QT interval should be a collected value THEN do not derive.
 

ECG Parameters
Corrected QT Intervals

 
When not entered directly in the eCRF, corrected QT intervals by Bazett's (QTcB) and Fredericia's (QTcF) formulas will be calculated, in msec, depending on the availability of other measurements. QTcF or QTcB values entered by the site will always be presented in output.
 
IF RR interval (msec) is provided (or can be derived from HR) then missing QTcB and/or QTcF will be derived as:
 

$QTcB = \frac{QT}{\sqrt{\frac{RR}{1000}}}$ $QTcF = \frac{QT}{\sqrt[3]{\frac{RR}{1000}}}$
Handling of Multiple Measurements

 
If multiple ECG findings (interpretations/clinical significance) are collected at the same timepoint and categorised as Normal or Abnormal (Clinically Significant or not), the worst classification for each participant at the timepoint will be used in summary tables.
 

ECG Parameters
Laboratory Parameters

 
If a laboratory value which is expected to have a numeric value for summary purposes, has a non-detectable level reported in the database, where the numeric value is missing, but typically a character value starting with '<x' or '>x' (or indicated as less than x or greater than x in the comment field) is present, the number of decimal places in the observed values will be used to determine how much to add or subtract in order to impute the corresponding numeric value. Similarly, if a character value starting with '<=x' or '>=x' is present, x will be used as the corresponding numeric value. 
 
Example 1: 2 decimal places: '< x' becomes x – 0.01
 
Example 2: 1 decimal places: '> x' becomes x + 0.1
 
Example 3: 0 decimal places: '< x' becomes x – 1
 
Example 4: 2 decimal places: '<= x' becomes x
 
Example 5: 1 decimal places: '>= x' becomes x
 
Example 6: 0 decimal places: '<= x' becomes x
 
 
 
Corrected calcium will be calculated, by GSK Biostatistics as:
 
 
Corrected Calcium [mmol/L] = Serum Calcium [mmol/L] + 0.02 * (40[g/L] – Serum Albumin[g/L])
 
Where Normal Serum Albumin = 40 [g/L]

 
eGFR (estimated Glomerular Filtration Rate) will be calculated by GSK Biostatistics at all timepoints, this will also be provided directly by the vendor at screening. The GSK calculated value at screening will be used as primary for reporting (e.g. will be used as baseline if appropriate).
 
The calculation will be as follows:
 
 
SI Results MDRD (GFR) (ml/min/1.73m^2) = 175 * (PD9S3/88.4) power -1.154 * Age power - 0.203 * Race * Sex
 
Where PD9S3 = Serum Creatinine (UMOL/L), Race = 1.212 for Black & 1.000 for other, Sex = 1.00 for males and 0.742 for females.

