**Footnotes:**

[figure not shown]
- 1 Potential clinical importance is defined in Section 15.8 for each relevant safety endpoint.
- 2 The Complete 4-domain Mayo score is used for the primary endpoint due to its wider dynamic range for assessment of dose-response compared to the Adapted Mayo score used for secondary and exploratory endpoints.
- 3 Clinical response and remission for the various iterations of Mayo score are defined in [Appendix 7](#), Section 15.7.
- 4 Symptomatic remission is defined as a rectal bleeding subscore of 0, and a stool frequency subscore of  $\leq 1$ , with no worsening from baseline.
- 5 Taper period is defined from the start of the taper (Weeks 12 or 24, respectively, for the Double-Blind and Open Label Extended Treatment Phases) to completion of the respective Extended Treatment Phases.

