## 15.8. Appendix 8: Values of Potential Clinical Importance

### 15.8.1. Laboratory Values

Haematology				
Laboratory Parameter	Units	Category	Clinical Concern Range	
			Low Flag (< x)	High Flag (>x)
Hematocrit	Ratio of 1	Male	0.201	0.599
		Female	0.201	0.599
Hemoglobin	g/L	Male	80	180
		Female	80	180
		Δ from BL	↓25	
Lymphocytes	Gl/L		0.8	
Neutrophils Absolute	Gl/L		1.5	
Platelet Count	Gl/L		100	550
White Blood Cell Count (WBC)	Gl/L		3	20
Eosinophil	Gl/L			>=1

Clinical Chemistry				
Laboratory Parameter	Units	Category	Clinical Concern Range	
			Low Flag (< x)	High Flag (>x)
Albumin	mmol/L		30	55
Calcium	mmol/L		2	2.75
Creatinine	mmol/L	Δ from BL		↑26
Glucose	mmol/L		3.5	7.9
eGFR	ml/min/1.73m 		60	
Potassium	mmol/L		3	5.5
Sodium	mmol/L		130	150
Total protein	g/L		50	85
Urea nitrogen	mmol/L			10.5
CRP	Mg/L			30

Liver Function				
Test Analyte	Units	Category	Clinical Concern Range	
ALT/SGPT	U/L	High	≥ 2x ULN	
AST/SGOT	U/L	High	≥ 2x ULN	
AlkPhos	U/L	High	≥ 2x ULN	
T Bilirubin	μmol/L	High	≥ 1.5xULN	
T. Bilirubin + ALT	μmol/L U/L	High	1.5xULN T. Bilirubin + ≥ 2x ULN ALT	

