### 15.8.3. ECG

ECG Parameter	Units	Clinical Concern Range	
		Lower	Upper
Absolute			
Absolute QTc Interval	msec		> 450
Absolute PR Interval	msec	< 110	> 220
Absolute QRS Interval	msec	< 75	> 110
Change from Baseline			
Increase from Baseline QTc	msec	> 30	≤ 59
	msec	≥ 60	

Categories for QTc summaries			
ECG Parameter	Units	Range for each category	
		Lower	Upper
Absolute			
Absolute QTcB and QTcF Interval	msec	< 450	
		≥ 450	≤ 479
		≥ 480	≤ 499
		≥ 500	
Change from Baseline			
Change from Baseline in QTcB and QTcF	msec	< 30	
		≥ 30	≤ 59

Categories for QTc summaries			
ECG Parameter	Units	Range for each category	
		Lower	Upper
		≥ 60	

Note that < 450 msec in Absolute and <30 msec in Change from Baseline QTcB/QTcF are not of clinical concern

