3.44.	Safety ETP	UR1	Summary of Worst-Case Urinalysis Results by PCI Criteria Post-Baseline Relative to Baseline for Extended Treatment Phase	ICH E3	SAC
3.45.	Safety OL I	UR1	Summary of Worst-Case Urinalysis Results by PCI Criteria Post-Baseline Relative to Baseline for Open Label Induction Phase	ICH E3	SAC
3.46.	Safety OL ETP	UR1	Summary of Worst-Case Urinalysis Results by PCI Criteria Post-Baseline Relative to Baseline for Open Label Extended Treatment Phase	ICH E3	SAC

Safety: Tables					
No.	Population	IDS / Example Shell	Title	Programming Notes	Deliverable [Priority]
ECG					
3.47.	Safety	EG1	Summary of ECG Findings for Induction Phase	IDS	SAC
3.48.	Safety ETP	EG1	As above for Extended Treatment Phase		SAC
3.49.	Safety OL I	EG1	As above for Open Label Induction Phase		SAC
3.50.	Safety OL ETP	EG1	As above for Open Label Extended Treatment Phase		SAC
3.51.	Safety	EG2	Summary of Change from Baseline in ECG Values by Visit for Induction Phase		None
3.52.	Safety ETP	EG2	As above for Extended Treatment Phase		None
3.53.	Safety OL I	EG2	As above for Open Label Induction Phase		None
3.54.	Safety OL ETP	EG2	As above for Open Label Extended Treatment Phase		None
3.55.	Safety	EG10	Summary of Maximum QTc Values Post-Baseline Relative to Baseline by Category for Induction Phase	IDS	SAC
3.56.	Safety ETP	EG10	As above for Extended Treatment Phase	Footnote: "Note: Induction phase baseline used"	SAC
3.57.	Safety OL I	EG10	As above for Open Label Induction Phase	Footnote: "Note: Induction phase baseline used"	SAC
3.58.	Safety OL ETP	EG10	As above for Open Label Extended Treatment Phase	Footnote: "Note: Induction phase baseline used"	SAC
3.59.	Safety	EG11	Summary of Maximum Increase in QTc Values Post-Baseline Relative to Baseline by Category for Induction Phase	Rationale: disclosure IDS	SAC

Safety: Tables					
No.	Population	IDS / Example Shell	Title	Programming Notes	Deliverable [Priority]
3.60.	Safety ETP	EG11	As above for Extended Treatment Phase	Footnote: "Note: Induction phase baseline used"	SAC
3.61.	Safety OL I	EG11	As above for Open Label Induction Phase	Footnote: "Note: Induction phase baseline used"	SAC
3.62.	Safety OL ETP	EG11	As above for Open Label Extended Treatment Phase	Footnote: "Note: Induction phase baseline used"	SAC
Vital Signs					
3.63.	Safety	VS1	Summary of Change from Baseline in Vital Signs for Induction Phase	ICH E3	SAC

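### SAP 15.6.4 derives RR (msec) from heart rate with the wrong formula, so any QTc built on it is inflated several-hundred-fold or more; two unit labels in 15.8.1 also conflict with 15.6.4

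*SAP*

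**What the plan says.** SAP 15.6.4 (ECG Parameters) has a fallback for records where RR is not supplied. RR in msec is derived as `(1/HR)/1000`, with the explanation "i.e. 1 / heart rate where the heart rate is taken as part of the ECG". The formula and the explanation already differ, because the explanation has no division by 1000.

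The derived RR then feeds the correction formulas: "IF RR interval (msec) is provided (or can be derived from HR) then missing QTcB and/or QTcF will be derived as" QT/sqrt(RR/1000) for Bazett and QT/cuberoot(RR/1000) for Fridericia. Two provisions limit the scope. Manually read ECGs are meant to use a collected RR, and "QTcF or QTcB values entered by the site will always be presented in output".

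SAP 2.2, footnote 1, links this to the primary safety endpoint: "Potential clinical importance is defined in Section 15.8 for each relevant safety endpoint". Section 15.8.3 sets the summary categories for "Absolute QTcB and QTcF Interval" (below 450, 450–479, 480–499, 500 or more) and for change from baseline (below 30, 30–59, 60 or more). The outputs include Table 3.55, "Summary of Maximum QTc Values Post-Baseline Relative to Baseline by Category for Induction Phase", and Table 3.59, "Summary of Maximum Increase in QTc Values Post-Baseline Relative to Baseline by Category for Induction Phase".

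On units, SAP 15.8.1 has the row "Creatinine mmol/L" with a limit of a 26-unit rise, and gives albumin limits of 30 and 55, also in mmol/L. In 15.6.4 the eGFR formula takes creatinine in umol/L, and the corrected-calcium formula takes albumin in g/L with a normal value of 40.

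**The concern.** A beat-to-beat interval in msec is 60,000 divided by the rate per minute. The printed rule lacks the factor of 60 and divides by 1000 where it should multiply. The correction formulas themselves are right: they expect RR in msec and convert it to seconds. The error therefore sits in one line but passes into every QTc computed through it.

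QTc findings of potential clinical importance are part of a primary endpoint. Tables 3.55 and 3.59 classify each participant by a maximum, so one derived post-baseline value is enough to set that participant's absolute category.

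The unit conflict is smaller. Neither the creatinine nor the albumin limit can sensibly be applied in the unit printed beside it.

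**Working it through.** **Inputs.** The RR rule and the QTcB and QTcF formulas come from SAP 15.6.4, and the categories from SAP 15.8.3. Heart rate is taken in beats per minute; SAP 15.8.4 gives that unit for vital signs, and the ECG unit is not stated separately. The QT and HR values are illustrative. The plan contains no worked QTc example to reproduce.

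**Size of the RR error.** Correct RR divided by printed RR is

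(60000/HR) / ((1/HR)/1000) = 60000 × 1000 = 60,000,000.

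HR cancels, so the factor is the same for every record. Because RR is in the denominator of both formulas:

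- QTcB is inflated by sqrt(60,000,000) = 7,746.
- QTcF is inflated by cuberoot(60,000,000) = 391.5.

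**Can another reading rescue it?** At QT 400 msec and HR 60:

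| Reading of the rule | RR (msec) | QTcB | QTcF | Inflation, B / F |
|---|---|---|---|---|
| As printed, (1/HR)/1000 | 0.0000167 | 3,098,387 | 156,595 | 7,746 / 391.5 |
| The explanation, 1/HR | 0.0167 | 97,980 | 15,659 | 245 / 39.1 |
| (1/HR) × 1000 | 16.67 | 3,098 | 1,566 | 7.75 / 3.91 |
| As printed, HR in beats per second | 0.001 | 400,000 | 40,000 | 1,000 / 100 |
| 60000/HR | 1000 | 400 | 400 | 1 / 1 |

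Only the last row works. The mildest wrong reading still puts any true QTcF above 500/3.91 = 128 msec in the top category. A second point under the printed rule: QT 330 at HR 100 gives QTcF 153,172 instead of 391. A fault in reading the PDF does not explain the error, because the explanation in words also lacks the factors 60 and 1000.

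**Effect on change categories (QTcF, printed rule).**

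- *Baseline and post-dose both derived:* the true change is multiplied by 391.5. A true rise of 60/391.5 = 0.15 msec reaches the 60-or-more category, and a true fall of 5 becomes −5 × 391.5 = −1,957, classed below 30.
- *Baseline entered (400), post-dose derived (true 400):* 156,595 − 400 = +156,195, classed 60 or more with no true change.
- *Baseline derived (true 400), post-dose entered (470):* 470 − 156,595 = −156,125, so a true rise of 70 is classed below 30.

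**Units.** The eGFR formula in 15.6.4 divides creatinine in umol/L by 88.4. On that factor, a rise of 26 umol/L is 26/88.4 = 0.29 mg/dL, while 26 mmol/L is 26,000/88.4 = 294 mg/dL. Albumin limits of 30 and 55 bracket the SAP's normal of 40 only in g/L. The total protein row in the same table (50 to 85) is in g/L.

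**The case against.** The strongest reply is that this is a typographical slip in a rarely used fallback. Protocol 8.6.3 requires machines that calculate heart rate and measure QTc automatically, entered QTc takes precedence, and manually read ECGs should not use the rule. The documents do not show that any record would reach it. If one did, a QTc in the hundreds of thousands would be obvious in a listing. QTc stopping decisions use averaged site readings (Protocol 7.1.4 and 8.6.3), so participant management does not depend on it, and safety data are not formally tested.

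Most of this stands as a limit on reach. It does not show that the fallback is idle. The protocol has each participant use a single correction formula throughout, while the SAP categorises both QTcB and QTcF and fills whichever is missing. If a site enters only its chosen formula, the other must be derived. RR is not among the machine outputs named in Protocol 8.6.3; if it is not collected, heart rate is the only route the SAP offers. The eCRF fields are not in the documents, so this cannot be settled from them.

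It is also fair to say that a masked increase is not wholly lost. In the example above, 470 msec still exceeds the absolute 450 msec criterion in 15.8.3, and Listings 28 and 29 would show it. What fails is the change category.

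The unit point is purely editorial: the limits work if stored umol/L and g/L values are compared with them directly.

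**Conclusion.** The RR formula is wrong as written, and no available reading makes it right. With ECG heart rate in beats per minute (assumed), it inflates QTcB 7,746-fold and QTcF 391-fold whatever the heart rate. Any absolute QTc derived from it at a physiological QT falls in the 500 msec or higher category, and change categories involving a derived value cannot be trusted. The effect is confined to records where RR is not supplied and QTc is not entered. Their number is unknown. Because the rule serves a primary safety endpoint and costs almost nothing to correct, it should be fixed even though gross values would probably be noticed. The creatinine and albumin labels are a genuine inconsistency, but they add nothing to the severity. No error is claimed in the other limits of 15.8.

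**What to change.** In SAP 15.6.4, replace the RR rule and its explanation with RR (msec) = 60000/HR, stating that HR is the ECG heart rate in beats per minute. In SAP 15.8.1, relabel creatinine as umol/L and albumin as g/L to match 15.6.4. Check that the ECG derivation program uses the corrected formula. The cost is one formula, two unit labels and one program check.

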13. Greater than 20 mg/day oral prednisolone (or equivalent, see SRM), or a change in dose of corticosteroid within 2 weeks prior to baseline endoscopy, or anticipated

inability to maintain a stable dose of corticosteroids (≤ 20 mg oral prednisolone or equivalent, see SRM) until Week 12.

14. Topical (rectal) corticosteroids or topical (rectal) aminosalicylate within 2 weeks prior to baseline endoscopy.
15. Initiation or a change in dose of mercaptopurine or azathioprine (including initiation or discontinuation of allopurinol) or methotrexate within 8 weeks prior to baseline endoscopy.
16. Treatment with ciclosporin, tacrolimus or thalidomide within 4 weeks prior to baseline endoscopy.
17. Treatment with an anti-TNF biologic within 8 weeks prior to baseline endoscopy, anti-integrin or anti-IL-12/23 biologics within 12 weeks prior to baseline endoscopy, or a JAK inhibitor within 4 weeks prior to baseline endoscopy.
18. A history of inadequate response, loss of response, or intolerance to more than three classes of approved advanced therapies for UC (including anti-TNF therapies, anti-integrin therapies, anti-IL-12/23 monoclonal antibodies, or JAK inhibitors; but excluding exposure within a clinical trial setting), of which participants must not have had inadequate response (primary non-response) to more than two classes.
19. Received faecal microbiota transplantation within 4 weeks prior to baseline endoscopy.
20. Received live vaccination within 4 weeks of Day 1 or plan to receive during the study until Follow-Up.

PRIOR/CONCURRENT CLINICAL STUDY EXPERIENCE

21. The participant has participated in a clinical trial and has received an investigational product within the following time period prior to the screening endoscopy day in the current study:
 - a. Biologics: 3 months, 5 half-lives, or twice the duration of the biological effect of the investigational product (whichever is longer);
 - b. New Chemical Entities (NCEs): 30 days, 5 half-lives or twice the duration of the biological effect (whichever is longer).

DIAGNOSTIC ASSESSMENTS*

22. Absolute neutrophil count $<1.5 \times 10^9/L$ or a haemoglobin $<80 \text{ g/L}$ or lymphocyte count $<0.8 \times 10^9/L$.
23. Estimated glomerular filtration rate (GFR) by Chronic Kidney Disease Epidemiology Collaboration equation (CKD-EPI) calculation $<60 \text{ ml/min}/1.73\text{m}^2$ at screening.

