## 2.2. Study Objectives and Endpoints

Objectives	Endpoints
Primary 
 
• To evaluate the safety and tolerability of repeat doses of GSK2831781 during the Double-Blind Induction Phase.
 
• To characterise the efficacy dose-response of GSK2831781 during the Double-Blind Induction Phase.
 
	
 
• Incidence of adverse events and serious adverse events during the Double-Blind Induction Phase.
 
• Incidence of findings of potential clinical importance during the Double-Blind Induction Phase for: 
 
◦ Vital signs.
 
◦ Clinical laboratory values (haematology, clinical chemistry and urinalysis).
 
◦ QTc.
 
 
 
• Change from baseline in Complete 4-domain Mayo score at Week 10.
 

Secondary 
 
• To evaluate the safety and tolerability of repeat doses of GSK2831781 during the Double-Blind Extended Treatment Phase.
 
	
 
• Incidence of adverse events and serious adverse events in the Double-Blind Extended Treatment Phase.
 
• Incidence of findings of potential clinical importance during the Double-Blind Extended Treatment Phase for: 
 
◦ Vital signs.
 
◦ Clinical laboratory values (haematology, clinical chemistry and urinalysis).
 
◦ QTc.
 
 
 

 
• To investigate the effect of repeat doses of GSK2831781 on clinical efficacy including endoscopic mucosal healing during the Double-Blind Induction Phase.
 
	
 
• Adapted Mayo endoscopic score of 0 or 1 at Week 10.
 
• Adapted Mayo clinical remission at Week 10.
 
• Adapted Mayo clinical response at Week 10.
 
• Symptomatic remission over time.
 
• Change from baseline in partial Mayo score over time.
 
• Change from baseline in Adapted Mayo endoscopic score and Ulcerative Colitis
 

Objectives	Endpoints
	Endoscopic Index of Severity (UCEIS) at Week 10.

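### Entry is screened at eGFR 60 by CKD-EPI, but the SAP derives eGFR by MDRD and flags values below 60 without naming an equation, so the two limits need not pick out the same participants

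*SAP*

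**What the plan says.** **Entry.** Protocol Section 5.2, exclusion 23, excludes participants below 60 mL/min/1.73 m² at screening, measured as "Estimated glomerular filtration rate (GFR) by Chronic Kidney Disease Epidemiology Collaboration equation (CKD-EPI) calculation".

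**Reporting.** SAP 15.6.4 (Laboratory Parameters) says that eGFR "will be calculated by GSK Biostatistics at all timepoints, this will also be provided directly by the vendor at screening". The formula's label opens "SI Results MDRD (GFR", and its coefficients include "Sex = 1.00 for males and 0.742 for females". Where both screening values exist, "The GSK calculated value at screening will be used as primary for reporting", with use as baseline given as an example where appropriate.

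**Flag.** The clinical chemistry table in SAP 15.8.1 gives eGFR a low limit of 60 and no equation.

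**Status of the flag.** SAP 2.2 lists "Incidence of findings of potential clinical importance" in clinical laboratory values during Double-Blind Induction under the primary safety objective. The footnote to that table says: "Potential clinical importance is defined in Section 15.8 for each relevant safety endpoint". The eGFR limit therefore feeds a primary safety endpoint. It is displayed in Table 3.31 (worst-case chemistry by PCI criteria relative to baseline) and in Listings 24 and 25.

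**The concern.** The SAP's low limits for several other laboratory parameters repeat the entry limits. Exclusion 22 uses neutrophils below 1.5, haemoglobin below 80 and lymphocytes below 0.8, and SAP 15.8.1 flags the same three values. For those parameters an eligible participant met the limit at entry, so a later flag records a fall below it. eGFR follows the same pattern with 60, but the change of equation breaks the link: the same creatinine result can give one answer at entry and another in the PCI display.

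The protocol guards against this for QTc. Section 8.6.3 requires one correction formula per participant for eligibility and for discontinuation, fixed from screening. Nothing comparable is written for eGFR.

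At stake is how a primary safety display reads. With one equation, a baseline below 60 would mean that renal function had moved between screening and Day 1. With two, a reader cannot tell that from a difference between formulas.

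**Working it through.** There is no stated figure to reproduce. The check compares the texts, works out what the SAP's formula implies, and traces the result through the displays.

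**1. Inputs.** Entry: CKD-EPI, limit 60 (Protocol 5.2); coefficients and version not given. Reporting: MDRD, all timepoints (SAP 15.6.4). Flag: below 60, equation not named (SAP 15.8.1). Baseline: latest non-missing pre-dose value (SAP 5.2). The schedule has clinical chemistry at screening and pre-dose on Day 1, so Day 1 will usually be the baseline.

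**2. Creatinine at which the SAP's formula gives 60.** With Cr in µmol/L, R = 1.212 for Black and 1.000 for other participants, and S = 1.00 for men and 0.742 for women:

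eGFR = 175 × (Cr/88.4)^−1.154 × Age^−0.203 × R × S

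Setting eGFR to 60 and solving:

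Cr₆₀ = 88.4 × (175 × Age^−0.203 × R × S / 60)^(1/1.154)

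For a non-Black man aged 40: 40^−0.203 = 0.4729; 175 × 0.4729 = 82.76; 82.76/60 = 1.379; 1.379^(1/1.154) = 1.321; 1.321 × 88.4 = 116.8.

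| Participant | Creatinine at MDRD = 60 (µmol/L) |
|---|---|
| Non-Black man, 40 | 116.8 |
| Non-Black man, 60 | 108.8 |
| Non-Black woman, 40 | 90.2 |
| Non-Black woman, 60 | 84.0 |
| Black man, 40 | 138.0 |
| Black woman, 40 | 106.5 |

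**3. What a different entry equation does.** Take the man with the 116.8 cut-off, and let C be the creatinine at which CKD-EPI gives 60 for him.

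- If C is above 116.8, a creatinine between 116.8 and C makes him eligible by CKD-EPI and below 60 by MDRD on the same sample.
- If C is below 116.8, he can enter just under C, and his creatinine can then rise past C without a flag until it passes 116.8.
- Only if C equals 116.8 do the limits coincide. Nothing in the documents shows that they do, for him or for any other profile.

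C cannot be calculated from the documents, so neither the direction nor the width of the gap is claimed.

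**4. Through the displays.** MDRD applies at every visit. With age treated as fixed over Induction, unchanged creatinine gives unchanged eGFR.

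- *Change from baseline:* consistent, since one formula is used throughout.
- *Table 3.31:* a participant already below 60 by MDRD at baseline starts in the low category and cannot be counted as newly low. One who starts higher by MDRD than by CKD-EPI needs a larger fall to be counted. The equation thus fixes the baseline category and who can move.
- *Listings 24 and 25:* these select on PCI values, so the equation determines which eGFR values and participants appear.

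**The case against.** The strongest reply is that nothing obliges the reporting equation to match the entry equation, and that preferring the sponsor's value is itself a consistency measure. The vendor's eGFR is described only for screening, so using it as baseline would mix sources. The SAP also does not name the vendor's equation; that it is CKD-EPI is inferred from exclusion 23. This stands as a reason to use one formula at all visits. It gives no reason for that formula to be MDRD when entry used CKD-EPI at the same limit.

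Three stronger readings are tempting, and the documents do not support them.

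- *The equation alone creates post-baseline shifts.* It does not. MDRD is used before and after dosing, so unchanged creatinine leaves the category unchanged.
- *Reported eligibility will contradict the safety tables.* SAP 4.5 takes inclusion/exclusion deviations from the eCRF page, not from derived eGFR, and no listed display compares the two.
- *SAP 2.1 should have declared the change.* The protocol names CKD-EPI only for eligibility, gives no eGFR equation for safety reporting, and leaves PCI definitions to the analysis plan. There was no planned reporting equation to depart from.

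It is also fair that eGFR is one of many PCI parameters, that creatinine has its own change-from-baseline flag that depends on neither equation, that safety data are not formally tested, and that the formula is the same in every arm.

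**Conclusion.** The mismatch is real, unexplained and minor. The same limit of 60 is applied through two equations, so participants who pass at entry and participants who are unflagged at baseline need not be the same people. The effect is confined to the eGFR baseline category, to who can be newly counted below 60 in Table 3.31, and to the PCI listings. It concerns participants close to the limit.

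A reader might want to put a band on how close. The documents do not allow it, because the CKD-EPI coefficients and version are absent; any width or direction would be assumed. Nor do they support a claim of bias between arms. The conclusion rests on the text and on the general point that two equations need not agree at 60. It does not depend on any assumed gap.

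**What to change.** Derive eGFR for baseline and PCI flags at all visits with CKD-EPI, in the version the vendor used at screening. Confirm that version with the vendor and name it in SAP 15.6.4 and beside the limit in 15.8.1. Keep MDRD as a supplementary display only if wanted.

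If MDRD must stay as the reporting equation, name it in 15.8.1, give the reason, and report how many participants were eligible by CKD-EPI but below 60 by MDRD at baseline.

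The cost is one re-programmed derivation and a re-run of the affected chemistry displays. Creatinine, age, sex and race are already inputs to the SAP's formula, so no new data are needed. Eligibility decisions are not reopened.
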